Achieving the US President's Emergency Plan for AIDS Relief (PEPFAR) goal of an AIDS-free generation has been re-emphasized in PEPFAR 3.0¹. The current recommendations of triple antiretroviral therapy (ART) for all HIV-positive pregnant and breastfeeding women regardless of CD4 count (Option B+)² requires that, beginning with the first antenatal care visit, HIV-infected mothers strictly adhere to a continuum of care known as the “prevention of mother-to-child transmission of HIV (PMTCT) cascade”. The PMTCT cascade includes attendance to regular clinic visits (at a minimum for ART refills), delivery in a health facility, and testing of the HIV-exposed infant (HEI) at six weeks, at 9 months and at the end of all breastfeeding (between 18-24 months). In a recent meta-analysis of loss to follow-up (LTFU) across the PMTCT cascade, about 50% of HIV+ pregnant women are already LTFU by delivery; within 3 months of delivery 33.9% of mother-infant pairs are also LTFU.³ Consequently, half of pediatric infections are currently estimated to occur in the postpartum period during breastfeeding and fewer than 40% of HEI are tested for HIV at 2-3 months.^{4,5} Thus, to achieve an AIDS free generation, effective strategies to improve outcomes of ART in maternal and child health (MCH) clinics are imperative to reduce LFTU among HIV-infected women and their infants and fully maximize adherence to ART. Determinants of this poor performance occur at multiple levels: healthcare delivery systems, providers, and beneficiaries (HIV-infected mothers). Current efforts to improve retention has mainly focused on patient-levels factors. Little is known about the characteristics of health delivery systems or specific health delivery system strategies that will improve long term outcomes of therapy in women who start lifelong ART in MCH clinics.

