Sample size and Justification: The traditional rule of thumb for sample size in logistic and Cox regression is ten events per predictor.⁷¹⁻⁷³ However, more recent simulation studies have revealed that serious problems aren't experienced until the number drops below five events per predictor.⁷⁴ Given the close association between logistic, Cox, and proportional odds regression models, these studies should provide a reasonable benchmark for sample size determination for our study. Thus, we adopted a rule of seven events per predictor in determining an appropriate sample size. Assuming that 1 contextual-level factor, 2 clinic-level factors, and seven patient-level factors (one socioeconomic, one cognitive, one psychological, one social, one related to accessibility to clinics, and one related to health status) will be significant at the 0.20 level in bivariate proportional odds models and that we'll need five additional terms due to polynomial trends or predictor-by-time interaction effects, our initial models for backward selection will require 105 events. We anticipate that 20% will be lost to follow-up in the first six weeks and 5% will be lost each year thereafter. Thus, for our loss to follow-up model we only require 378 participants.

However, we expect a cumulative MTCT rate of 5% by 24 months that suggests we will need 2,100 participants for this analysis assuming complete follow-up. Accounting for the expected drop-out, we will need to recruit $2100/(0.8*0.95*0.95) = 2,909$ participants. Assuming an average of 10 HIV diagnoses per year at eligible clinics, we will need to enroll in about 105 MCH clinics (3 per districts) in the first three years of the study.

C. Measurement / Instrumentation

Outcomes and measurement: Key programmatic outcomes that will be considered include: loss-to-follow-up (the proportion of HIV+ pregnant women initiated on ART for whom the whereabouts is unknown), retention in care (proportion of participants who are known to be receiving care), non-adherence to scheduled visits (proportion of participants whose whereabouts is unknown or who are in care but have missed at least one scheduled visit over the evaluation period), virological suppression (undetectable viral load), and MTCT rates (proportion of infants born to participating women who are tested positive for HIV).

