Table 1. Outcomes and definitions

Outcomes	Definition
Primary	
loss-to-follow-up	Proportion of HIV+ pregnant women initiated on ART for whom the whereabouts is unknown
Timely infant HIV diagnosis	Proportion of HIV-exposed infant with an appropriate HIV test result
Secondary	
Timely ART initiation	Proportion of HIV-infected participants (mother and infant) initiated on ART within two weeks of diagnosis
Retention in care	Proportion of participants who are known to be receiving HIV care
Non-adherence to scheduled visits	Proportion of participants whose whereabouts is unknown or who are in care but have missed at least one scheduled visit over the evaluation period
Virological suppression	Proportion of participants with undetectable viral load
MTCT rates	Proportion of infants born to participating women who tested positive for HIV
Survival	Proportion of participants known to be alive

For key laboratory tests, CD4 count is generally available free of charge at decentralized locations (over 70 MCH clinics) in Kinshasa and is done at HIV diagnosis and every six months. Viral load measurement is accessible at the national reference laboratory in downtown Kinshasa at a subsidized cost of \$25 or at private facilities (Dream, Doctors Without Borders—MSF) at higher cost per test and is recommended for every patient on ART at least once a year. We have budgeted this to ensure that each participant has at least one viral load measurement at enrollment and every year thereafter during this study.

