Healthcare system delivery characteristics and measurements: The Facility Audit of Service Quality (FASQ) will be adapted to assess the key organization characteristics of HIV care (including lifelong ART) delivery in participating MCH clinics. FASQ is a relatively low cost approach developed, by MEASURE Evaluation, for district level monitoring or service availability and quality.⁶⁸ It provides information on the type of services; status and functionality of infrastructure, equipment and quality of care. The key areas covered include: 1) the range of services offered (HIV testing and counseling, lifelong ART, laboratory), staffing and staff qualifications, operating hours, community linkages, selected administrative and quality control procedures; 2) Facility infrastructure (privacy/capacity, laboratory, delivery, well-child clinics); 3) Readiness to provide quality care in six areas: family planning; STI management; antenatal care; maternal/delivery care and post abortion care; child health/welfare; and HIV prevention, treatment, and care; and the digital maps of facilities and services available. This survey of health facilities participating in the study will be repeated every year thereafter (to monitor change). In each facility, individual-level patient characteristics including: socio-demographic and economic characteristics, beliefs about the health services (cost, quality), cognitive factors (knowledge about HIV and ART, perceived susceptibility and perceived benefit of early ART, perceived self-efficacy for adherence, perceived need for ART and other HIV services), psychological factors (e.g. depression, fear of stigma), social factors (social support – friends, family, male partner involvement in MCH care, intimate partner violence), accessibility to the clinics (distance, transportation, waiting time), and evaluated health status (WHO stage, CD4 count) will also be collected through face to face interviews at enrollment (within one month of ANC registration), after delivery (2-3 days in postpartum ward), at 6 weeks (6 weeks post-partum visit), at 24 weeks (end of exclusive breastfeeding period), and every six months thereafter through the end of all breastfeeding exposure at 24 months. Data on evaluated health status will come from mother-infant pair register. We will use the same research nurses who successfully interviewed and followed 991 mother-infant pairs in our breastfeeding study, at delivery, 1 week, and monthly thereafter and in our just completed conditional cash transfer study.^{16,33}

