gaps in the service delivery. The team will develop a priority action plan to address the main gaps and agree on a set of key indicators representing critical points in the PMTCT cascade that will be used to monitor the changes resulting from the implementation of the action plan. Thereafter, the health district QI team and a study team member will visit each clinic at least once a month to supervise and support the implementation of the action plan. Every quarter, using data from the monitoring system (Aim 1), the study team working with the provincial coordination of the National AIDS Program (cPNLS) will generate a quarterly report including a color-coded dashboard for tracking changes using the 'traffic light' approach. An indicator will score green when the target has been achieved, yellow/amber when there is a progress from the baseline value without reaching the target, and red when there is no progress or downward movement. Figure 6 outlines the cascade that was followed in South Africa and highlights the indicators used at critical points in the cascade to support tracking progress and identification of gaps in service delivery.¹⁴ A similar cascade will be created with indicators agree upon with the QI teams. The report will be generated for each participating clinics in the intervention group and shared with the cPNLS, the QI teams, and the management of the clinic. QI teams will be brought together to review these indicators, share experience, identify remaining gaps in the service delivery, and develop a new priority action plan for the next quarter.

Statistical Analysis –Aim 1: The primary outcomes for this aim are loss to follow-up and MTCT over the first 24 months of follow-up. Since the characteristics of interest in this aim may vary with time and a substantial proportion of participants may drop out prior to study conclusion or MTCT, both outcomes will be modeled using a proportional odds model for discrete time survival data.⁶⁹ At each follow-up time, the proportional odds model assumes that the log-odds that an event (loss to follow-up or MTCT) has occurred by that time point is a linear function of a time-dependent intercept plus covariates, some of which are time-varying. The model also assumes that the odds ratio comparing two different levels of a covariate is constant over time (i.e., proportional odds).

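### Aim 1 regresses event status by each visit on time-varying covariates with no risk set or timing rule, so modelled loss can fall; it also leaves out district clustering

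*Combined protocol and SAP*

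**What the plan says.** Section III.D (Statistical Analysis, Aim 1) names a proportional odds model for discrete-time survival data, for two outcomes: loss to follow-up and MTCT over 24 months. It then defines the model: the log-odds that the event "has occurred by that time point is a linear function of a time-dependent intercept plus covariates, some of which are time-varying", with one odds ratio over all visits. It gives no risk set, no lag and no rule for covariates after loss. Clustering is handled by GEE at clinic level. The Aim 2 paragraph names both district and clinic.

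The covariates have two main sources (section III.C). Most patient factors are collected "through face to face interviews at enrollment (within one month of ANC registration"), then after delivery, at 6 and 24 weeks, and six-monthly to 24 months. Facility factors come from a survey: "This survey of health facilities participating in the study will be repeated every year thereafter (to monitor change"). Table 1 defines loss as "Proportion of HIV+ pregnant women initiated on ART for whom the whereabouts is unknown".

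Section III.B supplies the rates: "We anticipate that 20% will be lost to follow-up in the first six weeks and 5% will be lost each year thereafter", and for MTCT "we expect a cumulative MTCT rate of 5% by 24 months". It also budgets for "five additional terms due to polynomial trends or predictor-by-time interaction effects".

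**The concern.** Once a woman is lost, or an infant infected, the cumulative event cannot be undone. A model of cumulative status whose covariates move with time does not respect that: when a harmful factor disappears, the modelled probability of already having had the event can drop. An interaction with time lets the effect vary but does not stop this.

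For loss there is a second problem. A woman whose whereabouts are unknown cannot be interviewed, so no loss event has a same-visit interview value. An earlier value must be substituted for every event, and the estimate depends on the rule. For MTCT the mother can still be interviewed, so the issues there are the possible fall in modelled risk and the use of covariates measured after the event.

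Third, clinics are sampled three to a district and a contextual predictor is expected. Standard errors that ignore the district are too small for predictors constant within it, if outcomes correlate within districts.

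At stake is which factors Aim 1 reports as associated with loss and MTCT. The plan wants these to guide where and how the intervention is scaled up.

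**Working it through.** **Plan figures reproduced (III.B).** Events: 7 × (1 + 2 + 7 + 5) = 105. Cumulative loss: 1 − 0.8 × 0.95 × 0.95 = 0.278. Loss model: 105 / 0.278 = 377.7, so 378. MTCT model: 105 / 0.05 = 2,100, and 2,100 / 0.722 = 2,908.6, so 2,909. These agree with the plan and are not in dispute.

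**Can modelled loss fall?** Take the plan's loss as the curve for women without the factor: 20% at 6 weeks, 1 − 0.8 × 0.95 = 24% a year later, 27.8% after two years. If the factor is present at one visit and gone at a later one, modelled loss falls when the odds ratio (OR) exceeds the ratio of the two baseline odds.
- 6 weeks to one year later: (0.24/0.76) / (0.20/0.80) = 1.26.
- 6 weeks to two years later: (0.278/0.722) / 0.25 = 1.54.
- OR 2: odds at 6 weeks 0.25 × 2 = 0.5, so 33.3%, then 24.0% once resolved.
- OR 1.2: odds 0.30, so 23.1%, then 24.0%; no fall.

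**MTCT.** Outcomes come from the register, which records infant tests at 6 weeks, 9 months and 18 months (III.C). The Background says "half of pediatric infections are currently estimated to occur in the postpartum period during breastfeeding". Assume 2.5% by delivery and the other 2.5% even over 104 weeks: F(t) = 0.025 + 0.025 × t/104.
- F at 6, 39 and 78 weeks: 2.64%, 3.44%, 4.38%. Odds: 0.02716, 0.03560, 0.04575.
- Thresholds: 0.03560/0.02716 = 1.31 and 0.04575/0.03560 = 1.29.
- Postpartum share 30%, F(t) = 0.035 + 0.015 × t/104: 1.14 and 1.15. Share 70%, F(t) = 0.015 + 0.035 × t/104: 1.67 and 1.49.

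**Missing interview values.** Of 2,909 women, 2,909 × 0.278 = 809 are expected lost by 24 months and 2,909 × 0.20 = 582 (72% of them) by 6 weeks. The latter have only an enrollment and perhaps a delivery interview.

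**Effect of the substitution rule.** This was simulated with the plan's loss rates and a binary factor with no effect on loss (true OR 1). Assumptions: starting prevalence 30%, drifting to 25% or 20%, with values correlated between visits. Ranges cover different drift shapes and layouts with and without a separate delivery interview, except the second row (no separate delivery interview).

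| Data layout | OR, drift to 25% | OR, drift to 20% |
|---|---|---|
| Rows kept after loss, last value carried forward | 1.11 to 1.16 | 1.24 to 1.32 |
| Rows kept after loss, previous-visit value | 1.08 to 1.10 | 1.15 to 1.19 |
| Risk set, last value carried forward | 1.03 to 1.05 | 1.05 to 1.11 |
| Risk set, previous-visit value | 0.99 to 1.01 | 0.99 to 1.01 |

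With no drift the first layout gives 1.01; with enrollment values only, the cumulative model gives 0.99 to 1.01.

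**District clustering.** There are 2,909/105 = 28 women per clinic and 2,909/35 = 83 per district, so 83 − 28 = 55 women in the other two clinics. Assume clinic ICC 0.05 and district ICC ρ of 0.01, 0.02 or 0.03. For a district-constant predictor, clinic-only SE / correct SE = √[(1 + 27 × 0.05) / (1 + 27 × 0.05 + 55ρ)] = 0.900, 0.825, 0.766.
- Actual level at nominal 0.10, 2 × [1 − Φ(1.645 × ratio)]: 13.9%, 17.5%, 20.7%.
- At nominal 0.20 (1.282 in place of 1.645): 24.9%, 29.0%, 32.6%.
- Clinic-level predictor with within-district correlation 0.3 (assumed; 55 × 0.3 × ρ): 11.2%, 12.3%, 13.5% at nominal 0.10.
- ρ = 0: ratio 1, no inflation.

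**The case against.** The plan uses survival language and cites a method for discrete-time survival data, chosen partly because women may drop out. That source may define a risk set, and a risk set alone removes roughly two-thirds or more of the simulated bias. This stands as a limit on size. But the formula written is cumulative, and an analyst following the text would fit that.

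The missing-value problem concerns interview-based patient factors, whereas Aim 1 is chiefly after health-system factors, which the annual survey records whether or not a woman is lost. This also stands. A reader might infer that all Aim 1 associations are biased; the documents do not support that. The simulated bias needs drift in prevalence, carry-forward and rows kept after loss, none of which the plan states.

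A reader might also evaluate MTCT at the interview dates, or from delivery, and get different thresholds. The plan takes its outcomes from the register, so the infant-test times are the relevant ones.

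On clustering, facilities are sampled within every one of the 35 districts, so for inference to present-day Kinshasa the districts can be seen as strata. The plan gives no ICC and never says that its one contextual factor is constant within a district. That narrows the point to district-constant or similar predictors. It does not explain why district is accounted for in Aim 2 and not in Aim 1, when the findings are meant to inform scale-up.

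**Conclusion.** The point holds as a defect in the stated Aim 1 model, worth correcting before analysis. The incoherence follows from the written formula and the plan's own loss rates: a resolving factor with OR above 1.26 over the year after 6 weeks makes modelled loss fall. The MTCT thresholds, about 1.31 and 1.29, rest on the assumed timing of infection.

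The spurious association for loss is conditional. It is an OR of about 1.11 to 1.16 or 1.24 to 1.32 under the assumed drifts with rows kept after loss, and much smaller with a risk set. It is not material without drift or with enrollment values. A lag without a risk set does not remove it; the two together do.

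The clustering omission inflates the 0.10 rule to about 14% to 21% and the 0.20 rule to 25% to 33% for district-constant predictors under assumed ICCs. It matters little for clinic-level predictors and not at all if the district ICC is zero.

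A reader might take this as a flaw in the trial's effectiveness result. It is not: the randomised Aim 2 comparison uses a different analysis, which already accounts for district.

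**What to change.** In the Aim 1 analysis text, replace the cumulative definition with a discrete-time hazard: the log-odds of the event in each interval among those event-free at its start (pooled logistic regression). Take time-varying covariates from the previous visit, or from the last facility survey before the interval. For MTCT, set the intervals by the register's infant-test times. If cumulative odds are preferred, restrict covariates to enrollment and Phase I values, which gives up the time-varying information the plan wants.

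Use district as the GEE cluster for Aim 1, with a small-sample correction for 35 districts, for example the Mancl-DeRouen variance with a t reference. In simulation under the assumed ICCs, uncorrected district clustering still ran the 0.10 rule at 12.3% to 12.6%; with the correction it ran at 9.5% to 10.3%.

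This is a change of SAP text using the same data and standard software. The costs are that odds ratios refer to interval risk rather than cumulative status (a different estimand), covariates are one visit older, and intervals for district-level predictors are wider. The sample sizes of 378 and 2,909 come from an events-per-predictor rule and do not change.

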
Questionnaires for survey and other interviews are under development and will be submitted for approval once finalized.

D. Detailed study procedures

Intervention – CQI interventions: In MCH clinics randomized to the intervention group, QI initiatives using participatory data-driven approaches and on-site monitoring and supervisory support, will be implemented. At each site, a QI team will be established from among the facility staff (at least one staff each from ANC service, delivery/maternity service, and well-child service). Health district level QI teams will also be set up to ensure oversight of the health facilities' QI initiatives. After randomization, QI teams will be brought together and provided with the baseline data to help them identify

[figure not shown]

Fig 6 Prevention of mother-to-child transmission cascade with associated indicators (ANC = antenatal care; ARV = antiretroviral; HAART = highly active antiretroviral therapy; AZT = zidovudine; PCR = polymerase chain reaction). Bhardwaj et al. S Afr Med J 2014 Mar;104(3 Suppl 1):239-43.

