We will use a backward selection methodology to build a proportional odds model for each outcome consisting of contextual, clinic-level, and patient-level predictors. Within clinic-level clustering will be accounted for using Generalized Estimating Equations (GEE). Given the large volume of predictors being considered in this aim, we will only include predictors in our initial models for backward selection if significant at the 0.2 level in a bivariate (single predictor) model. At each step of backward selection, variables insignificant at the 0.1 significance level will be removed from the model.

Statistical analyses – Aim 2: The frequencies of outcomes will be compared between the intervention and control groups using adjusted Pearson's Chi-square.⁷⁷ All analyses will be intent-to-treat, meaning that women will be kept in their randomized group independent of whether they actually received (or did not receive) all their care in the group. The intervention and control groups will be compared for baseline prognostic factors and any imbalances that persist after randomization will be adjusted for using logistic regression. Within district- and clinic-level clustering will be accounted for using GEE.

Human subjects' involvement and characteristics

This study will involve HIV-infected pregnant women and their HIV-exposed infants who receive care in one of the maternal and child health clinics providing HIV care in Kinshasa. Clinical record of those participants (mother-infant register) will be accessed by the study team to extract data for the outcomes. In addition those mother will be interviewed on regular basis on sensitive subject

related to their HIV status, social support including relationship with partner. In addition to the discomfort associate with the discussion of such personal topic, there is a potential risk for confidentiality breach associated with the study.

To minimize those risk, all study staff will be retrained on ethical conduct of human subject research. As part of PEPFAR funded routine services for gender-based violence, resource are available at the level of those MCH clinic to provide psychological support for participant who might need them.

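### Aim 1 allows for clustering by clinic but not by district, so tests of district-level predictors, and to a lesser degree of clinic factors shared within a district, are too liberal if clinics in a district are correlated

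*Combined protocol and SAP*

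**What the plan says.** Under Statistical Analysis – Aim 1 (section III.D), loss to follow-up (LTFU) and mother-to-child transmission (MTCT) over 24 months are modelled by discrete-time proportional odds. Predictors enter if significant at 0.2 singly and are removed if not significant at 0.1. On clustering the paragraph says "Within clinic-level clustering will be accounted for using Generalized Estimating Equations (GEE"). The Aim 2 paragraph that follows says "Within district- and clinic-level clustering will be accounted for using GEE".

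The Aim 1 procedure is to "build a proportional odds model for each outcome consisting of contextual, clinic-level, and patient-level predictors". The term contextual is not defined, and randomised arm is not named among the predictors.

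On timing, the method is justified by "Since the characteristics of interest in this aim may vary with time", and the log-odds are "a linear function of a time-dependent intercept plus covariates, some of which are time-varying". Section III.A places collection of facility characteristics in Phase I, before randomisation. Section III.C repeats the facility survey yearly; its content includes "staffing and staff qualifications, operating hours, community linkages, selected administrative and quality control procedures".

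**The concern.** Districts are the randomisation unit. Each contributes about three clinics, and district bodies supervise them. Clinics in one district may therefore have more similar outcomes than clinics in different districts. A variance estimator clustered on clinic treats the three clinics as independent. For a predictor with the same value in all three, it counts 105 independent units where there are 35. Aim 2 recognises the district level; Aim 1 does not.

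Aim 1 is meant to identify delivery factors that show where and how to scale up the continuous quality improvement (CQI) intervention (section II). Tests that are too liberal for district-shared factors would put more inert factors on that list than the stated thresholds imply.

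A second issue depends on what the sponsor intends. CQI changes facilities: at each intervention site "a QI team will be established from among the facility staff", and "the health district QI team and a study team member will visit each clinic at least once a month". If facility values measured after randomisation enter Aim 1 without an arm term, a factor that has come to differ by arm can pick up part of any CQI effect.

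**Working it through.** **1. The plan's own figures.** Section III.B counts 1 + 2 + 7 factors plus 5 extra terms, which is 15. Seven events per term gives 7 × 15 = 105 events.
- Retention is 0.8 × 0.95 × 0.95 = 0.722, so LTFU is 27.8% and 105/0.278 = 377.7, or 378.
- MTCT needs 105/0.05 = 2,100, and 2,100/0.722 = 2,908.6, or 2,909.

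All are reproduced, and none depends on the clustering level. Per clinic this is 2,909/105 = 27.7 women for LTFU and 2,100/105 = 20 for MTCT.

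**2. Closed form for a district-level predictor.** Let m be women per clinic, ρc the correlation within a clinic and ρd the correlation between clinics of one district. With three clinics per district,

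estimated SE / true SE = √{[1 + (m−1)ρc] / [1 + (m−1)ρc + 2mρd]}.

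The documents give no ICC, so the values are assumptions. For LTFU take m = 27.7 and ρc = 0.055; the numerator is 1 + 26.7 × 0.055 = 2.468.

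| ρd | Denominator | True/estimated SE | Inert factor passes 0.20 screen | Inert factor significant at 0.10 |
|---|---|---|---|---|
| 0.005 | 2.745 | 1.05 | 22% | 12% |
| 0.01 | 3.022 | 1.11 | 25% | 14% |
| 0.02 | 3.576 | 1.20 | 29% | 17% |
| 0.035 | 4.407 | 1.34 | 34% | 22% |

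**3. Simulation of the stated model.** 35 districts × 3 clinics; visit-specific intercepts; independence GEE; one inert factor per model; 4,000 trials per setting. ICCs are on the latent scale, with clinic and district together 0.055. LTFU rises from 20% to 27.8%; MTCT is assumed to be 2.5, 4 and 5% at successive visits. Entries are the share of trials significant at 0.10.

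| District-level factor, district ICC | 0 | 0.005 | 0.01 | 0.02 | 0.035 | With fix |
|---|---|---|---|---|---|---|
| LTFU | 11% | 12% | 13% | 16% | 21% | 10% |
| MTCT | 10% | 11% | 12% | 13% | 15% | 11% |

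- A clinic factor with within-district correlation 0.5, at ICC 0.01 and 0.035: 14% and 16% for LTFU (fix 11%); 12% and 13% for MTCT (fix 10–11%).
- A clinic factor uncorrelated within district: 12% at either ICC, so the district level adds nothing there.
- District clustering without a small-sample correction still rejects in 12–14%.

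The MTCT excess is smaller than the closed form would give because a latent-scale ICC implies less correlation on the observed scale for a rare event.

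**4. Could the district ICC be zero?** An unmodelled CQI effect assigned by district itself creates within-district correlation. With equal allocation its latent variance is (ln OR)²/4, against a logistic residual variance of π²/3 = 3.29. For an assumed OR of 0.75 this is 0.0207/3.311 = 0.006; for 0.6 it is 0.0652/3.355 = 0.019.

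**5. Secondary point: updated facility values without arm.** With equal arms and prevalences symmetric about 50%, an inert factor takes up a share of the CQI log-OR equal to the prevalence difference between arms. At an assumed CQI OR of 0.6, prevalences of 30/70, 40/60 and 45/55 (control/CQI) give spurious ORs of 0.6^0.4 = 0.82, 0.6^0.2 = 0.90 and 0.6^0.1 = 0.95. In simulation (2,000 trials per setting, district ICC 0.01) the factor, tested alone for LTFU, is significant at 0.10 in 48, 22 and 13% of trials. At OR 0.75 the figures are 25, 14 and 11%. With no CQI effect it is 10%. With arm and corrected district clustering it is 9–11%, with an OR of 0.99–1.00.

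**The case against.** The strongest reply has three parts.

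*The clustering effect is modest and narrow.* No ICC is given, contextual need not mean district-level, and only one such factor is counted among 15 terms. At ICCs of 0.005–0.01 the excess is two to three points for LTFU, and uncorrected district clustering (12–14%) would gain nothing. This stands as a limit on size. It also shows that the small-sample correction has to be part of the fix. It does not explain why Aim 1 should ignore a level that Aim 2 recognises.

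*The arm problem depends on a reading the text leaves open.* Section III.A says the two-phase design gives time to assess the delivery characteristics for Aim 1, and Phase I values are independent of arm in expectation. The time-varying covariates could be the patient factors re-interviewed at each visit. This stands. A reader might infer that Aim 1 is confounded by the intervention; the documents establish only that the survey wave is unspecified.

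*The single-factor figures do not describe the planned selection.* If a CQI component is itself surveyed and kept in the model, it acts as a proxy for arm. In a simplified check (800 trials, OR 0.6, 30/70) a 5/95 proxy cut rejection of the inert factor from 44% to 13%; a 20/80 proxy left 31%. This also stands: 48% must not be read as a retention rate for the multivariable backward selection.

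**Conclusion.** The clustering point holds, conditional on positive correlation between clinics of one district. Under the assumed ICCs, an inert district-level factor is significant at 0.10 in about 12–21% of trials for LTFU and 11–15% for MTCT, against 10–11% after the fix. The lower ends are barely above nominal; the upper ends need a district ICC of 0.02–0.035. The condition is plausible, since a CQI effect of the kind the trial seeks would by itself supply some of that correlation.

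A reader might infer that all Aim 1 standard errors are wrong, or that the trial comparison is compromised. Neither follows. Patient-level factors and clinic factors uncorrelated within district are essentially unaffected, and Aim 2 already allows for both levels.

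The arm term is secondary. It matters only if updated facility values are used, CQI affects the outcome and the factor comes to differ by arm. Its size ranges from near nominal (OR 0.75 with 40/60 or 45/55) to large (OR 0.6 with 30/70), on assumed inputs.

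**What to change.** In the Aim 1 analysis paragraph:

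1. Cluster the GEE on health district, with clinics nested within, using a small-sample-corrected robust variance (for example Kauermann–Carroll) and a t reference.
2. Define contextual predictors and the level at which they are measured.
3. State whether facility predictors are Phase I or updated values. With Phase I values alone no arm term is needed. With updated values, force randomised arm into every single-predictor screen and every selection step. If follow-up spans the start of CQI, force arm, period and arm-by-period.
4. Report factors that are CQI components as part of the intervention, not as independent determinants.

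No new data are needed. The costs are:

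- Intervals widen for district-shared predictors. In a 15-term model the t reference has 35 − 1 − 15 = 19 df. A 500-trial check found patient-level intervals about 6% wider and rejection of 8.8% in place of 10%, while the district factor fell from 18% to 11%.
- If arm is forced in, MTCT has 105/16 = 6.6 events per term, or 105/18 = 5.8 with the period terms. Both are below the plan's seven but above the five it cites. LTFU, with about 2,909 × 0.278 = 809 events, is not constrained.
- A factor nearly coincident with arm (10/90) cannot be separated from it: its SE rises about 70% and the corrected test still rejects in 12–14%.
- Using Phase I values alone avoids the arm problem but misses later change in facilities.
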